### 7.4. Exposure and Compliance

IP exposure and dosing information including the number of doses per subjects and amount of IP received will be tabulated by treatment arm and age group.

For each treatment, IP compliance will be summarized by compliance category ( $\leq 80\%$ , 80-120%,  $\geq 120\%$ ) and the number of subjects in each compliance category. Study medication compliance will also be summarized as a continuous variable using descriptive statistics. This

analysis will be conducted for the SAF population.

## 8. Efficacy Analysis

### 8.1. Primary Efficacy Analysis

#### 8.1.1. Primary Efficacy Endpoint

The primary efficacy endpoint is the change in the composite outcome of the pulmonary, cardiovascular, hematologic, renal, and nervous system sections of the snakebite severity score (SSS) from Baseline (pre-dosing) to the average of the scores from 6 and 9 hours after first dose: Change = (Baseline - [6hr + 9hr]/2).

The ITT population will be used to analyze the primary efficacy endpoint. For completeness the analyses will be repeated for the PP population.

Descriptive statistics for the SSS as well as the 6hr and 9hr mean scores will be tabulated by treatment group.

The primary analysis will use ANCOVA. A sensitivity analysis will use rank-regression applying the same adjustment covariates as specified in the ANCOVA. To better understand the appropriateness of applying a parametric vs. nonparametric approach, the CSR will include diagnostics plots of ANCOVA residuals.

The change from baseline to the average of the 6hr and 9hr scores will be compared between treatment groups using an ANCOVA with the baseline SSS score, subject age group, the presence or absence of baseline neurotoxic symptoms, and country as covariates. The varespladib-methyl to placebo (varespladib-methyl vs. placebo) will be compared at the 5% two-sided significance level; corresponding 95% two-sided confidence interval for the difference will be presented.

Six sets of subgroup analyses will be performed: (1) patient age, (2) baseline neurotoxic symptoms, (3) prior receipt of antivenom, (4) country, (5) snake type, and (6) timing of receipt of study drug. The following paragraphs describe these six sets of subgroup analyses.

1. *Patient age.* Summary statistics, including baseline SSS and least square means from the ANCOVA, will be presented separately for pediatric (5 to 17 years) and adult ( $\geq 18$  years) subjects. If the study includes too few children to fit an ANCOVA, only summary statistics will be presented.

2. *Baseline neurotoxic symptoms.* The treatment effect will be estimated in subjects with and without moderate or severe neurotoxic symptoms at baseline (SSS nervous system score of 0-1 vs. 2-3). These analyses will be analogous to those described for the pediatric and adult subgroup analyses, except that the ANCOVA will include age group, but not neurotoxicity.

3. *Prior receipt of antivenom.* The treatment effect will be estimated separately in subjects who have and have not completed an initial dose of antivenom prior to initiation of study drug. These analyses will be analogous to those described for the pediatric and adult subgroup analyses, except that the ANCOVA will include age group but not receipt of antivenom prior to initiation of study

drug.

4. *Country*. The treatment effect will be estimated in separately in subjects enrolled in the U.S. and those enrolled in India. These analyses will be analogous to those described for the pediatric and adult subgroup analyses, except that the ANCOVA will include age group but not country.

5. *Snake type*. The treatment effect will be estimated separately in subjects bitten by vipers, elapids, and unknown snake types. These analyses will be analogous to those described for the pediatric and adult subgroup analyses, except that the ANCOVA will include age group.

6. *Timing of receipt of study drug*. The treatment effect will be estimated separately in subjects for whom the time from bite or symptom onset to receipt of study drug was <5 hours and >5 hours. These analyses will be analogous to those described for the pediatric and adult subgroup analyses, except that the ANCOVA will include age group.

There will be several sensitivity analyses.

Sensitivity analysis will be conducted for the primary efficacy analysis (1) adding completion of the initial dose of antivenom prior to the initiation of study drug as a covariate and (2) using a compressed SSS as the outcome and applying the same analytic methods as described above. A separate set of analyses will estimate the effect of treatment on individual component subscores of the SSS.

Other sensitivity analyses will estimate the treatment effect on the primary endpoint excluding data from one site at a time. For this analysis, data from sites that enrolled 10 patients or fewer will be combined and excluded as a single group. The purpose of this sensitivity analysis is to assess whether data from any single site has an outsized effect on the estimated treatment effect of the primary endpoint.

Another sensitivity analysis will apply the tipping point approach described in [Section 6.1.4.3](#).

Sensitivity and subgroups analyses of the primary and key secondary endpoints will not be part of the gatekeeping procedure for hierarchical testing of endpoints.

### 8.1.2. Key Secondary Efficacy Endpoints

The ITT population will be used to analyze the secondary efficacy endpoints. All secondary endpoints will be analyzed using the prespecified assessment timepoints according to the protocol. All statistical models for change from baseline in a particular endpoint will include covariates for baseline value of the particular endpoint, baseline SSS, baseline neurotoxicity (Yes, No; based on the SSS neurological system subscore), age group (5-17, 18+), and country (U.S. vs. India). Key secondary endpoints will be tested sequentially using a fixed-sequence gatekeeping procedure for the hierarchical testing of multiple endpoints. The significance of the treatment effect for the primary endpoint (i.e., change in SSS from baseline to average at 6 and 9 hours) will be the first hypothesis tested, using a significance level of 0.05. If the null hypothesis for the primary endpoint is rejected, then the first key secondary endpoint (i.e., AUC of SSS through Day 7) will be tested, also with a significance level of 0.05. If the null hypothesis for this test is rejected, the second key secondary endpoint (total antivenom use) will be tested ( $\alpha=0.05$ ).

If the null hypothesis for this test is rejected, the third key secondary endpoint (AUC of NPRS through Day 3) will be tested ( $\alpha=0.05$ ). If the null hypothesis for this test is rejected, the fourth key secondary endpoint (CGI-I at Day 2) will be tested ( $\alpha=0.05$ ). Sensitivity and subgroups analyses of the primary and key secondary endpoints will not be part of the gatekeeping procedure for hierarchical testing of endpoints.

#### **8.1.2.1. AUC of the Pulmonary, Cardiovascular, Local Wound, Hematologic Symptoms, Renal, and Nervous System Sections of the SSS from Baseline Through Day 7**

The SSS-AUC7d will be compared between treatment groups within an ANCOVA model with the baseline SSS score, age group (5 to 17 years,  $\geq 18$  years), baseline neurotoxicity, and country as covariates. The comparison of varespladib-methyl to placebo (varespladib-methyl vs. placebo) will be tested at a 5% two-sided significance level; the corresponding 95% two-sided confidence intervals will be presented. The AUC will be calculated according to [Section 6.1.7.2](#). Also note that this SSS score is calculated only using the pulmonary, cardiovascular, local wound, hematologic, renal, and nervous system subscores. A reduction in SSS-AUC (i.e., negative parameter estimate) will represent a faster improvement in snake bite symptoms on average. Individual subscore AUCs by treatment group will also be summarized using descriptive statistics. Subgroup analyses will estimate the treatment effect separately for pediatric and adult patients, for patients with and without clinically significant neurotoxicity, for patient who have and have not completed an initial dose of antivenom prior to randomization, for the U.S. and for India, for each snake type (viper, elapid, and unknown), and for patients for whom the time from bite or symptom onset to receipt of study drug was  $<5$  hours and  $\geq 5$  hours.

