### **6.1.2. Adjustments for Covariates**

The comparison of the primary and secondary efficacy endpoints between the varespladib-methyl and placebo groups for the primary efficacy analysis will be adjusted for four variables: (1) baseline SSS composed of the pulmonary, cardiovascular, hematologic, renal, and nervous system sections treated as a continuous variable; (2) age group treated as a dichotomous variable (age 5-17 vs. age  $\geq$ 18 years); (3) baseline neurotoxicity (SSS neurological system subscore) treated as a dichotomous variable (0-1 vs.  $\geq$ 2); and (4) Country (U.S. vs. India). Because we anticipate low numbers of patients in the two pediatric age group strata, we have collapsed these two strata into a single group (age 5-17) for the purpose of data analysis. A sensitivity analysis for the primary and key secondary endpoints will include a fourth covariate: completion of the initial dose of antivenom prior to initiation of study drug (Yes or No).

The mixed model for repeated measurements (MMRM) will be adjusted for baseline SSS, baseline neurotoxicity, age group, completion of the initial dose of antivenom prior to initiation of study drug, and scheduled timepoint of assessment. It will also include terms for treatment-by-time interaction and baseline score-by-time interaction.

The Cox model to estimate the hazard ratios for all-cause mortality will be adjusted for baseline SSS, baseline neurotoxicity, age group, and completion of the initial dose of antivenom prior to initiation of study drug.

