### 6.1.7.2. SSS-AUC7d

The AUC calculation includes the pulmonary, cardiovascular, local wound, hematologic, renal, and nervous system sections of the SSS assessment up to 7±1 days. The calculation will include the baseline assessment. All assessments within baseline and baseline + 8 days will be included in the calculation. This endpoint will be analyzed according to the missing data procedures described in [Section 6.1.4](#) above.

In order to standardize the duration of time for each SSS-AUC7d calculation, the “Day 7” SSS will be set at exactly 168 hours regardless of when it was actually assessed for this endpoint, with two exceptions:

- 1) For patients whose “Day 7” score was assessed prior to Day 7 (prior to 144 hours) and whose score is higher at the “Day 14” assessment than at the “Day 7” assessment, we will linearly interpolate between the “Day 7” and “Day 14” scores to impute the score at 168 hours.
- 2) For patients whose “Day 7” occurs on Day 10 or later (240 hours), we will linearly interpolate between “Day 3” and “Day 7” to impute the score at 168 hours.

The AUC will be calculated using the trapezoidal rule: average the SSS scores between two adjacent timepoints, multiply by the difference in time points in hours, repeating this across all time points and summing the results to obtain the total AUC across a fixed range of time. Thus the AUC at a particular timepoint  $j$  is calculated as follows.

$$AUC_j = \frac{1}{2}(SSS_j + SSS_{j-1})(t_j - t_{j-1})$$

where  $t$  is measured in hours;  $j = 1, \dots, J$ ; and  $J$  is the total number of timepoints at which SSS is measured.  $J = 6$  if all planned SSS assessments are performed. Thus the total AUC for subject  $i$  from baseline to Day 7 is as follows.

$$AUC_{i, \text{BL to Day 7}} = \frac{1}{2} \sum_{j=1}^J (SSS_{i,j} + SSS_{i,j-1})(t_{i,j} - t_{i,j-1})$$

Thus AUC is calculated for each subject with baseline and post-baseline SSS scores, subject to the constraints on missingness described above. An example of this applied in SAS is provided at [lexjansen.com/wuss/2004/posters/c\\_post\\_the\\_sas\\_calcuations\\_pdf](http://lexjansen.com/wuss/2004/posters/c_post_the_sas_calcuations_pdf)

- where: The SSS assessments  $SSS_0, SSS_1, \dots, SSS_J$  are made at times  $t_0, \dots, t_J$
- $t_0$  is the time of the initiation of the IV infusion
- $SSS_0$  is the SSS assessment at baseline

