#### **Key Secondary Efficacy Endpoint #1, SSS-AUC**

```
Proc mixed data=ADMI alpha=0.05;
  By _imputation_;
  Where PARAM="Primary Outcome SSS-AUC through Day 7" and AVISIT="Day
    7";
```

```
Class TRT01PN(ref='0') AGEGR2BL(ref='5 to 11  
years') NEUROBL(ref='No') COUNTRY(ref='India');  
model AVAL = TRT01PN SSSBL AGEGR2BL NEUROBL COUNTRY;  
lsmeans TRT01PN / cl pdiff;  
run;  
proc mianalyze data=Estimates alpha=0.05;  
modeleffects estimate;  
stderr StdErr;  
run;
```

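### The plan does not settle which baseline score adjusts the six-section SSS-AUC, and its only explicit definition omits local wound

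*SAP*

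**What the plan says.** **Outcome.** SAP 6.1.7.2: "The AUC calculation includes the pulmonary, cardiovascular, local wound, hematologic, renal, and nervous system sections of the SSS assessment". SAP 2.2.1.2 and 8.1.2.1 agree, and SAP 4.2 names local wound as what distinguishes this endpoint from the primary.

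**Covariate, general definition.** SAP 6.1.2 opens with "The comparison of the primary and secondary efficacy endpoints between the varespladib-methyl and placebo groups" and lists, as its first adjustment variable, "baseline SSS composed of the pulmonary, cardiovascular, hematologic, renal, and nervous system sections treated as a continuous variable". Local wound is not in it.

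**Covariate, endpoint section.** SAP 8.1.2.1 fits the comparison "within an ANCOVA model with the baseline SSS score", with age group, baseline neurotoxicity and country. Later in the paragraph, after pointing to the AUC calculation, it adds that "this SSS score is calculated only using the pulmonary, cardiovascular, local wound, hematologic, renal, and nervous system subscores".

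**Rule for key secondaries.** SAP 8.1.2 says models for change from baseline "will include covariates for baseline value of the particular endpoint, baseline SSS, baseline neurotoxicity" and other terms. An AUC is not a change from baseline.

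**Code.** In SAP 8.1.3 the SSS-AUC model has one baseline score, SSSBL. The same name appears in the antivenom, NPRS-AUC and CGI-I models and is defined nowhere. The SSS-AUC step selects the parameter "Primary Outcome SSS-AUC through Day 7".

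**The concern.** A baseline covariate earns its place by predicting the outcome, and the natural choice here is the baseline of the same score. Under 6.1.2 the outcome would contain local wound and the covariate would not. Local wound of 3 or more is enough for entry on the score criterion (Protocol 8.2.1 and Appendix A), so a patient can enter with a five-section baseline of 0 and a six-section baseline of 3 or 4. The five-section covariate cannot tell that patient from one with no local wound.

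The label adds a second risk. The primary model in 8.1.3 uses the words Primary Outcome for the five-section score, so a programmer could select a five-section AUC for this test.

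This is the first gate after the primary (SAP 8.1.2). If it fails, antivenom use, NPRS-AUC and CGI-I at Day 2 are not formally tested. SAP 4.1 calls the study confirmatory, so an alpha-protected test should have one identifiable model.

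**Working it through.** **1. Score ranges** (Protocol 10.3.1.1)
- Five sections (pulmonary, cardiovascular, hematologic, renal, nervous): 3 + 3 + 4 + 3 + 3 = 16, which matches the worst score in SAP 6.1.7.1.
- Six sections: 16 + 4 for local wound = 20.

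**2. The plan's own sample size** (SAP 3.2, primary endpoint only)
- Inputs: difference 1.1, SD 1.75, two-sided alpha 0.05, power 85%, 1:1.
- Two-sample t-test: 47 per arm = 94, power 85.4%. The normal approximation gives 46 per arm = 92. The stated 94 reproduces.
- No difference, SD, correlation or power is stated for SSS-AUC, so what follows rests on assumptions.

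**3. How much of the AUC is baseline itself**
If the first post-dose assessment is at 3.5 h, the baseline score has trapezoid weight 3.5/2 = 1.75 h, or 1.75/168 = 1.0%. Its value as a covariate therefore comes almost entirely from correlation with later scores.

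**4. Precision lost with the five-section baseline**
Let B5 be the five-section baseline, L baseline local wound and B6 = B5 + L. Let r6 be the correlation of the AUC with B6. Assume that baseline predicts the AUC only through the sum B6. Then
- r5 = r6 × corr(B5, B6)
- residual variance ratio = (1 − r5²)/(1 − r6²)
- power with B5 = Φ[(1.960 + 1.036)/√ratio − 1.960], if the B6 model has 85% power (an assumed benchmark).

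Worked cell: SD(L)/SD(B5) = 0.8, L and B5 uncorrelated, r6 = 0.5. Then corr(B5, B6) = 1/√(1 + 0.64) = 0.78; r5 = 0.39; ratio = (1 − 0.152)/(1 − 0.25) = 1.13; power = Φ(2.996/1.063 − 1.960) = 80.5%.

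Grid: SD(L)/SD(B5) from 0.4 to 1.0, and correlation of L with B5 from −0.3 to 0.3.

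| r6 | Residual variance ratio | Power with B5 |
|---|---|---|
| 0.3 | 1.01-1.06 | 83-85% |
| 0.5 | 1.04-1.22 | 78-84% |
| 0.7 | 1.10-1.63 | 65-82% |

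Across the grid corr(B5, B6) is 0.59-0.95. Age group, neurotoxicity and country are in both models and are not represented, so the correlations are best read as those remaining after adjustment for them.

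**5. Type I error**
In a simulated null trial (n = 94, 4,000 runs), ANCOVA rejected in 5.2% of runs with B5 and 4.6% with B6. The Monte Carlo standard error is √(0.05 × 0.95/4000) = 0.34%, so neither differs from 5% beyond chance.

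**The case against.** **The plan may already intend six sections.** In the body of 8.1.2.1 the outcome is called SSS-AUC or the AUC, and the only earlier SSS score is the baseline covariate. The six-section note can therefore be read as defining that covariate. Section 6.1.2 is also not applied literally elsewhere: 8.1.2.3 uses baseline NPRS in place of baseline SSS, 8.1.2.4 adds baseline CGI-I and 8.1.2.2 adds prior antivenom. Its opening sentence mixes secondary endpoints with the primary efficacy analysis. This stands, and it rules out the stronger inference that the plan definitely adjusts for five sections. But the note follows a sentence about calculating the AUC and can equally refer to that, in which case 6.1.2 is the only definition left.

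**The code proves nothing.** It is sample code. The five-section primary model uses BASE, not SSSBL, and the NPRS-AUC code uses SSSBL where the text specifies baseline NPRS. That is right: SSSBL cannot be tied to the five-section score, and the label does not show that a five-section AUC will be analysed. Both remain undefined or misleading.

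**The loss may be trivial.** The documents give no baseline distribution, so nothing shows that many patients enter on local wound alone or that it dominates their AUC. A reader might also suppose that local wound explains a further 10, 20 or 30% of variance and convert this to about 12, 28 or 47 extra patients on 110, using 110/(1 − R²) − 110. The range has no source, the formula needs shares of residual variance, and it describes adding a separate predictor, not replacing one sum by another. Those figures should not be used.

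**The grid favours six sections by construction.** It assumes that local wound predicts as strongly per point as the other sections. If local wound predicted little, the six-section sum could do worse. Entering local wound as its own term avoids that, at one degree of freedom.

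**Conclusion.** The point holds as an unresolved inconsistency. The only explicit definition of the baseline SSS covariate has five sections, the outcome has six, and neither the endpoint section nor the code says which baseline enters the model. Under 6.1.2, the missing baseline is that of the component the SAP uses to justify this endpoint.

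The likely cost is some precision and power in a gating test. Its size is unknown: on the assumptions above, power falls by 0 to 20 points from 85%, and by about 1 to 8 points at r6 = 0.5.

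Two further inferences are not supported. The five-section model would not discard baseline severity, because the five-section score is contained in the six-section one. It would also not bias the comparison or inflate type I error, because treatment is randomised and either covariate is measured at baseline. What remains is an efficiency question and an analytic choice left open in an alpha-protected test.

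**What to change.** Before unblinding:
- In SAP 6.1.2 and 8.1.2.1, state that SSS-AUC is adjusted for the six-section baseline SSS, or for the five-section baseline plus baseline local wound as a separate term. Choose one.
- In SAP 8.1.3, define SSSBL separately for each endpoint that uses it.
- Relabel the parameter so that the six-section AUC is unmistakably the one analysed.

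Baseline local wound is already collected (Protocol 10.2.2), so no new data are needed. The change is a few lines of SAP text and code. It follows the own-baseline approach of 8.1.2.3 and 8.1.2.4, and SAP section 1 places SAP approval before unblinding.

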#### **8.1.2.2. Total Differential Antivenom Requirement from Baseline through Day 28**

The total number of vials of antivenom administered will be analyzed using a proportional odds logistic regression with three ordered categories. For each type of antivenom administered, the number of vials of antivenom from baseline through Day 28 will be categorized as low, medium, or high. Cutoffs for these categories are based on recommendations regarding treatment for each antivenom type as well as a review of available blinded data.

##### India Polyclonal Antivenom (all antivenom administered in India)

- Low: 0 vials
- Medium: > 0 to 10 vials
- High: > 10 vials

##### CroFab

- Low: 0 vials
- Medium: > 0 to 6 vials
- High: > 6 vials

## ANAVIP

- Low: 0 vials
- Medium: > 0 to 10 vials
- High: > 10 vials

This model will use the following covariates: baseline SSS score, age group (5 to 17 years,  $\geq$  18 years), baseline neurotoxicity, receipt of antivenom prior to baseline (Yes, No), and country. The treatment effect will be summarized with an estimated odds ratio. The comparison of varespladib-methyl to placebo (varespladib-methyl vs. placebo) will be tested at a 5% two-sided significance level; the corresponding 95% two-sided confidence intervals will be presented. Subgroup analyses will estimate the treatment effect separately for pediatric and adult patients, for patients with and without clinically significant neurotoxicity, for patient who have and have not completed an initial dose of antivenom prior to randomization, for the U.S. and for India, for each snake type (viper, elapid, and unknown), and for patients for whom the time from bite or symptom onset to receipt of study drug was <5 hours and  $\geq$ 5 hours.

As an analysis of model fit, the assumption of proportional odds will be tested. An exploratory analysis will calculate a binomial logistic regression model collapsing the medium and high antivenom categories into a single category. The dependent variable will be either “low” or “medium or high” antivenom use. The model will use the same set of covariates described above.

### **8.1.2.3. AUC of the NPRS from Baseline Through Day 3**

An ANOCVA will be used to compare the NPRS-AUC3d for the two treatment groups with baseline NPRS score, age group (5 to 17 years,  $\geq$  18 years), baseline neurotoxicity, and country as covariates. The comparison of varespladib-methyl to placebo (varespladib-methyl vs. placebo) will be tested at a 5% two-sided significance level; the corresponding 95% two-sided confidence interval will be presented. The AUC will be calculated according to [Section 6.1.7.3](#). A reduction in NPRS-AUC (i.e., negative parameter estimate) will represent a faster average improvement in pain symptoms. Subgroup analyses will estimate the treatment effect separately for pediatric and adult patients, for patients with and without clinically significant neurotoxicity, for patient who have and have not completed an initial dose of antivenom prior to randomization, for the U.S. and for India, for each snake type (viper, elapid, and unknown), and for patients for whom the time from bite or symptom onset to receipt of study drug was <5 hours and  $\geq$ 5 hours.

